3.4. Clinical Data Collection

Where available, participating physicians in the study will be asked to provide the following clinicopathologic data in the provided case report form (CRF) for subjects meeting the inclusion criteria below. All data submitted to GenomeDx will utilize a case ID number and will be de-identified by the site prior to submission.

1. Ethnicity
2. Age at radical prostatectomy
3. Pre-operative PSA level: last pre-operative PSA level before radical prostatectomy
4. Lymph node status
5. Clinical and pathological stage
6. Clinical and pathological Gleason score (primary, secondary, and tertiary pattern if available)

7. Surgical margin status
8. Extra-prostatic extension
9. Seminal vesicle invasion
10. All available post-op PSA levels
11. Recommended treatment or management option for the patient after surgery
(detailed by type of treatment recommended)
12. Dates of actual treatments
13. Patient outcome

[figure not shown]

Figure 1: Study flow diagram

[figure not shown]

Figure 2: Patient flow timeline

4. Subject Eligibility

4.1. Inclusion Criteria:

Individuals satisfying all of the following criteria will be eligible to participate.

1. Prostate cancer patients who have undergone radical prostatectomy(RP)
2. PSA <0.1 ng/ml at enrollment
3. At least one of the following:
 - a. pT3 (SVI or EPE), **or**
 - b. Positive Surgical Margins
4. Tumor tissue (FFPE block) available for processing
5. RP within 1 year of enrollment
6. 18 years of age or older

4.2. Exclusion Criteria:

Individuals who satisfy **any** of the following criteria will not be eligible to participate.

1. Have regional or distant metastatic disease
2. Received any radiation or hormone therapy (neo-adjuvant, adjuvant, or salvage)
3. Node positive
4. Subjects who do not have banked specimens

5. Endpoints

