2.2. Secondary Objectives

1. To determine whether the decision impact of the GC test is of benefit to patients. Specifically, is net benefit of GC use superior to those who do not have the GC test as assessed by decision curve analysis.
2. To determine whether use of the GC test results in decreased likelihood of adjuvant treatment for subjects with high CAPRA-S score (≥ 5) and increased adjuvant treatment for subjects with low CAPRA-S score (< 5). The hypothesis is that there is a non-zero interaction between GC test use and CAPRA-S.
3. To determine whether GC use is associated with earlier use of salvage therapies in CAPRA-S low risk patients and later use of salvage therapy in CAPRA-S high-risk patients.

4. To determine whether use of GC results in improved protection from BCR and metastatic progression.
5. To investigate the impact of GC use on QOL, and whether there is differential QOL impact among CAPRA-S high- and low-risk patients.
6. To determine whether collaborative-wide education and the use of CAPRA-S scores in the control group impacts rates of adjuvant radiotherapy compared to historical controls.

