2.3. Exploratory Objective

1. To determine whether it is possible that use of GC will result in an overall reduced net cost to the healthcare system by avoiding treatment in many patients.

3. Study Design

This is a 4-5 year (up to 2 years enrollment , 3-year follow-up) prospective, cluster-crossover, unblinded, study of 550 subjects from at least fourteen centers of the Michigan Urological Surgery Improvement Collaborative (MUSIC), a physician-led quality improvement consortium comprised of the vast majority of urology practices within the state of Michigan.

According to the cluster-crossover design, each participating MUSIC clinical center within MUSIC will be randomized to either a Genomic Classifier care-based (GC) or Usual-Care-based (UC) strategy for a period of 3 months, during which all enrolled subjects within the center will be provided the assigned strategy. Random assignments will be generated centrally by a study statistician and provided to centers immediately before commencing enrollment in each 3-month period. The randomization will be based on a random block size of either 2 or 4. This will ensure that each center will have two periods of GC and two periods of UC during the enrollment period, maintaining study-wide balance and blinding of assignments in subsequent periods.

If enrolled during the GC period, both subjects and their treating physician will be provided GC (from GenomeDx) and CAPRA-S (from MUSIC-Central) to inform their treatment plan. In the UC periods, only the CAPRA-S results, provided by MUSIC-Central, will be available. Blinding of subjects and treating physicians will not be possible given the nature of the information.

Subjects enrolled to the GC arm will receive MUSIC-led education about the GC test. The pros and cons of the GC test need to be described by an unbiased clinician scientist including the past history of the test (published studies).

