5.2. Secondary Endpoints

The following secondary endpoints will be utilized:

1. Time (from randomization) to adjuvant treatment administration
2. Time (from randomization) to salvage treatment administration
3. Biochemical Recurrence (BCR) at 3 years
4. Metastatic disease (regional or distant) at 3 years
5. QOL measures currently collected as part of the MUSIC-PRO initiative (<http://musicurology.com/pro/>) at 3, 6, 12, and 24 months after surgery

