Secondary Objective 3: Time-to salvage therapy initiation will be modeled using a Cox formulation of a Frailty regression model with a similar formulation (ie: main and random effects) to that used for the primary analysis. Kaplan-Meier curves for GC and UC arms will be plotted, as well as for combinations of high- and low-risk GC and CAPRA-S groups.

Secondary Objective 4: Time-to BCR and metastatic progression will be evaluated similarly to the model described for Secondary Objective 3.

Secondary Objective 5: Summary statistics for all QOL instruments and corresponding confidence intervals will be calculated and compared for the GC and UC subjects and shown graphically over time. Validated instruments are used to measure erectile function, urinary function, sexual interest, and sexual satisfaction. Scores for each domain will be scaled with a minimum to maximum range of 0-100. Comparisons between GC and UC subjects will be made at each timepoint (3, 6, 12 and 24 months after surgery) and on each domain and overall score (VAS 0-10), using an ANCOVA analysis including adjustment for time since surgery. Should the assumptions for ANCOVA not be met (strongly skewed data or substantial ceiling or floor effect) a semiparametric ANCOVA model will be used (as in Buja 1989) to adjust for time-from surgery. If the distribution of time-from surgery is similar in the two groups, a Mann-Whitney test for differences will be used to corroborate the ANCOVA model. For this secondary objective, there will be no adjustment for multiple comparisons across domains or time points.

Exploratory Objective: Using a variety of budget models the cost of care for patients in the GC vs. UC arms will be compared out to 3 years from surgery. This will include estimated costs for adjuvant therapy. Differences in total cost, and differential cost per patient (UC vs GC) will be calculated and compared using either standard t-tests if data is normally distributed or appropriate non-parametric test if data is right skewed.

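### QOL arm comparisons at 3 and 6 months after surgery may include forms completed before the man had an arm

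*Combined protocol and SAP*

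**What the plan says.** - **Entry window.** Inclusion criterion 5 (Section 4.1) requires "RP within 1 year of enrollment". No minimum interval is stated.
- **When the arm is fixed.** Section 3.1 allocates each man to whichever arm his centre holds when he enrols. Section 3 releases the test result only after that: "If enrolled during the GC period, both subjects and their treating physician will be provided GC".
- **Objective.** Secondary Objective 5 (Section 2.2) is "To investigate the impact of GC use on QOL", and whether that impact differs by CAPRA-S risk.
- **Source and clock of the QOL data.** Section 5.2 uses "QOL measures currently collected as part of the MUSIC-PRO initiative", "at 3, 6, 12, and 24 months after surgery". Collection is therefore not started by trial entry. The time-to-treatment endpoints in the same list run from randomization.
- **Analysis.** Section 7.3 states: "Comparisons between GC and UC subjects will be made at each timepoint (3, 6, 12 and 24 months after surgery"), "using an ANCOVA analysis including adjustment for time since surgery". A semiparametric version is the fallback, with a Mann-Whitney test as corroboration if time from surgery is similar in the two groups.

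The visible text does not say whether a form completed before enrolment is excluded, flagged or used as a baseline. Figure 2 (patient flow timeline) is not shown in the copy reviewed.

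**The concern.** Two clocks are in use. QOL visits are counted from surgery, and the arm begins at enrolment, which may be up to 12 months later. A man who enrols after month 3 has a 3-month form that predates his arm; if he enrols after month 6, his 6-month form does too. Exclusion criterion 2 bars earlier radiation or hormone therapy, so these forms carry neither an effect of the GC result nor an effect of adjuvant or salvage treatment.

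Followed as written, the comparison at each visit can mix forms that could show an effect of GC use with forms that could not. The early differences would then be diluted toward zero. A null result at 3 or 6 months could be reported as no QOL impact when many of the forms had no chance of showing one. The same applies to any contrast by CAPRA-S group.

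**Working it through.** The plan gives no QOL effect size, standard deviation or power, so there is no figure of its own to reproduce. The 83% power at 350 subjects in Section 7.5.2 is for the primary test only.

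**Inputs.** From the documents: entry at 0 to 12 months after radical prostatectomy (RP) (Section 4.1); visits at 3, 6, 12 and 24 months after surgery (Sections 5.2 and 7.3); 550 subjects (Section 3). Assumed: the distribution of entry time E, and a lag L from enrolment to any QOL effect.

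**Step 1: share of forms predating enrolment at visit t.** This is P(E > t).
- Uniform entry over 0 to H months: 1 − min(1, t/H). For H = 12: 1 − 3/12 = 75% and 1 − 6/12 = 50%.
- Entry density falling linearly to zero at month 12: (1 − t/12)². This gives (9/12)² = 56% and (6/12)² = 25%.

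**Step 2: share of the true arm difference recovered if all forms are used and the effect starts at enrolment (L = 0).** This is one minus the share in step 1.

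| Assumed entry | Month 3: predate / recovered | Month 6: predate / recovered |
|---|---|---|
| All by month 3 | 0% / 100% | 0% / 100% |
| Uniform 0–6 | 50% / 50% | 0% / 100% |
| Falling linearly to zero at 12 | 56% / 44% | 25% / 75% |
| Uniform 0–9 | 67% / 33% | 33% / 67% |
| Uniform 0–12 | 75% / 25% | 50% / 50% |

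Uniform 0–12 is an upper scenario but not a strict ceiling: uniform entry over months 1 to 12 gives 9/11 = 82% and 6/11 = 55%.

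**Step 3: does the planned covariate help?** If time since surgery means surgery to form, it is nearly constant at a given visit and says nothing about the order of form and enrolment. If it means surgery to enrolment, a main effect still leaves the earlier forms in the arm contrast. A simulation bears this out (4,000 datasets per setting, 550 men at 1:1, true difference 0.24 SD chosen arbitrarily, form dates within half a month of the visit, no centre effects). With uniform 0–12 entry, about 25% of the difference is recovered at month 3 and 50% at month 6 under either reading. Restricting to post-enrolment forms recovers about 100%.

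**Step 4: does discarding forms cost more than it gains?** Let r be the share of forms after enrolment and q the share able to show an effect. The expected test statistic is proportional to q with all forms and to q/√r after restriction, a ratio of 1/√r while L is shorter than the visit time. For uniform 0–12 entry this is 1/√0.25 = 2.00 at month 3 and 1/√0.50 = 1.41 at month 6. For linearly falling entry it is 1/√0.4375 = 1.51 and 1/√0.75 = 1.15. If L is 3 months or more, q is zero at month 3 and restriction gains nothing there.

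As an illustration in power terms, assume an effect of 0.30 SD, 275 per arm and no clustering. Power is 94% if no form predates enrolment. If half do, it is 42% with all forms and 70% with post-enrolment forms only.

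**Step 5: later visits.** A man entering close to month 12 may complete his 12-month form at or just before enrolment. With L = 1 month and uniform 0–12 entry, month 12 recovers 11/12 = 92%. Month 24 always follows enrolment.

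**The case against.** The strongest reply is that nothing in the documents says pre-enrolment forms will be retrieved. Section 7.3 compares GC and UC subjects, and a man is neither until he enrols. Figure 2 may also show how enrolment and QOL visits line up. This stands in part: a reader might infer that the plan means to include these forms, and the text does not establish that. It is silent both ways. But the data come from a collection that runs independently of the trial, the comparison is specified at every visit, and the analysis text has no rule that would keep the forms out.

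A second reply is that most men will enrol early. Section 3.1 links consent to discussing the surgical pathology, and Section 7.5.1 builds accrual from monthly surgical case-loads. Both lean toward early entry and neither settles it. If entry is early, the dilution is small and the rule costs almost nothing.

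A third is that restricting forms could itself select. A centre's arm is issued before the period opens and enrolment is unblinded, so the interval from RP to enrolment could in principle respond to the arm. That is a fair limit on the fix. A reader might go further and infer that entry times do differ by arm. The documents do not show it: the crossover balances arms within centre, and Section 3 aims at "maintaining study-wide balance and blinding of assignments in subsequent periods". It is something to check, not a demonstrated bias.

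**Conclusion.** The gap is real and confined to Secondary Objective 5, mainly its 3- and 6-month comparisons. If pre-enrolment forms are used, the early arm differences are diluted toward zero, and the planned adjustment does not correct this. The size is illustrative because entry times are not given: no loss if all men enter by month 3, 44% and 75% of the difference recovered at months 3 and 6 under linearly falling entry, and 25% and 50% under uniform entry over 12 months. These figures assume that the effect starts at enrolment and that all forms are pooled.

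Three stronger readings are not supported. The primary test of the GC score effect does not use QOL data and is not affected. The time-to-treatment endpoints run from randomization, and no arm imbalance in entry time is shown that would call for changing their models. Nor does restriction help at every visit regardless of timing: month 3 may stay uninformative, because the assay, the report and any treatment all follow enrolment.

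This is a modest point about one of six secondary objectives, worth settling before the data are analysed.

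**What to change.** In Section 7.3, Secondary Objective 5:

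1. Restrict the between-arm comparison at each visit to forms dated after enrolment.
2. Adjust for months from RP to enrolment, and define time since surgery so that the two intervals are not confused.
3. Report by arm, for each visit, how many forms predate enrolment, together with the distribution of RP-to-enrolment time, so that any arm difference in entry timing can be seen.
4. Use the last pre-enrolment score as a covariate only in a supporting analysis. On the stated schedule, only men enrolled after their 3-month form would have one.

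**Cost.** The change is mostly wording. RP and enrolment dates are already needed for inclusion criterion 5. Form dates must be obtained from the QOL collection, since the case report form list in Section 3.4 does not name them. Fewer forms remain: of 550 men, before missing data, about 241 at month 3 and 412 at month 6 under linearly falling entry (550 × 0.4375 and 550 × 0.75), or about 138 and 275 under uniform 0–12 entry (550 × 0.25 and 550 × 0.50).

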5.1. Primary Endpoint

The Primary Endpoint will be whether the subject receives any adjuvant therapy (radiation and/or hormone therapy). Adjuvant will be defined as preceding BCR (i.e.: PSA \geq 0.2 ng/ml) and within 18 months of RP. Patients must have a PSA within 6 months prior to the receipt of radiotherapy.

5.2. Secondary Endpoints

The following secondary endpoints will be utilized:

1. Time (from randomization) to adjuvant treatment administration
2. Time (from randomization) to salvage treatment administration
3. Biochemical Recurrence (BCR) at 3 years
4. Metastatic disease (regional or distant) at 3 years
5. QOL measures currently collected as part of the MUSIC-PRO initiative (<http://musicurology.com/pro/>) at 3, 6, 12, and 24 months after surgery

5.3. Exploratory Endpoint

Cost comparison/difference between GC and UC care at 3 years after surgery

6. Assay Specimen Requirements and Logistics

6.1. FFPE Block Selection/Specimen Acquisition

FFPE (formalin fixed paraffin embedded) tissues from RP prostate tumor sample blocks will be collected from patients in both the GC and UC arms for transcriptome-wide expression analysis.

The FFPE block from the RP that exhibits a) highest Gleason Score, AND b) highest percent tumor involvement will be selected for sampling with at least 60% tumor by surface area. The pathologist will mark the H&E slide that will be used to guide punching. The marked area should preferentially sample tumor with the highest Gleason grade (e.g., in a 4+3 lesion, the pattern 4 component should be enriched in the punch specimen). Two (2) X 1.5 mm in diameter punches will be sampled from the RP FFPE block (e.g., using a tissue microarray core device or a disposable punch tool, to be provided by GenomeDx). Each punch will be placed in a separate microfuge tube and stored at 4°C until shipping.

6.2. Specimen Preparation and Annotation

GenomeDx will ship specimen kits for each patient sample. Pathologists will have the option of sending the FFPE block or using the provided punch tool to perform two core biopsy punches per specimen to be placed in the provided microfuge tube or slides in the provided slide carriers.

If FFPE block is sent, place the representative block into small zip lock bag provided.

1. Select one FFPE block representative of the tumor.

Choose a block with at least 0.5 cm² of tumor tissue with the highest Gleason grade of tumor. If multiple blocks exist, select the block with the highest percent tumor cells by area.

2. Please do not submit an H&E slide. GenomeDx will prepare an H&E slide on site.

If punch tool core biopsy method for FFPE radical prostatectomy blocks is used:

1. Identify a H&E slide that closely matches the block face. Cut and H&E stain a new slide, if multiple sections have already been cut from the block.
2. Circle the area with the highest Gleason grade on the corresponding H&E slide. a) The punch area should have a minimum of 60% tumor (by surface area)
3. Using the punch tool provided in the specimen kit, take two punches from the FFPE block which corresponds to the area circled on the H&E slide.
 - a) Two (2) x 1.5 mm diameter cores
 - b) Minimum length of tissue in the punched cores should be 2mm
4. Place each cores in a separate microcentrifuge tubes. Close the caps and seal tubes with Parafilm.
5. Document that punch contains > 60% tumor content on Specimen Profile Form.
6. Affix provided barcodes only to tubes containing specimens and number each tube to correspond with the Specimen Profile Form.

Duplicate cores may be requested by GenomeDx if specimen provided does not yield either sufficient RNA, cDNA or fails microarray quality control.

Microfuge tubes to be labeled with unique de-identified patient and specimen numbers (assigned by GenomeDx and matching the case numbers assigned along with the clinicopathologic details).

If submitting slides:

Please send five (5) x 5um thick unstained, uncharged sections plus one (1) H&E stained slide from the block as defined in our block selection criteria.

6.3. Specimen Logistics

1. Place FFPE block or microfuge tubes containing specimens into the foam insert in the specimen kit box provided
2. Place a copy of the completed requisition form in the plastic bag provided.
3. Place the provided coldpack on top of the foam insert, close the box and seal in a clear bag.

6.4. Specimen shipping instructions

Specimen kits are to be sent in a shipping box via FedEx (FedEx Account # to be provided upon

site enrollment) to the following address:

GenomeDx Biosciences

6.5. GenomeDx Decipher[®] Testing

GenomeDx will extract and purify RNA from submitted tumor specimens. If the sample fails to yield sufficient RNA (at least 100 ng) GenomeDx will request a duplicate specimen from the submitting physician (preferably from a different FFPE block for that patient). GenomeDx will then generate cDNA, amplify, label and hybridize it to oligonucleotide arrays. The Decipher gene signature tested will remain unchanged throughout the course of the study, such that all patients will undergo the identical assay.

GenomeDx will then perform QC on the raw microarray data. Samples that fail array QC will be re-amplified (provided there is sufficient RNA remaining). If there is insufficient RNA or the 2nd amplification fails, the duplicate sample will be extracted. After generation of the array data and QC analysis, GenomeDx will return (on dry ice) RNA or specimen cores not used for amplification to the pathologist or discard appropriately.

7. Statistical Considerations

7.1. Statistical Methods Supporting the Primary Objective

The Primary Objective of this study is to determine the impact of GC test result on adjuvant treatment decisions compared to clinical factors alone. This will be evaluated by testing for an effect of GC score in a regression model which adjusts for CAPRA-S risk score. As a cluster-crossover trial, a generalized linear mixed effects model will be used to model the probability of a subject receiving adjuvant treatment within center, in a specific period of the study. Since GC score is a subject-level covariate, an individual-level regression model is utilized rather than a cluster-level aggregated analysis (Campbell 2014, Chapter 6). Specifically, the model to be fit is

$$\text{logit}\left(\frac{\pi_{ijk}}{1-\pi_{ijk}}\right) = \beta_0 + \beta_1 G_i + \beta_2 (G_i * GC_i) + \beta_3 \text{CAPRA-S}_i + \gamma_j + \phi_k$$

where π_{ijk} is the probability of treatment for the i^{th} subject enrolled in the j^{th} cluster (ie: center) during the k^{th} period, G_i is the group to which the subject is enrolled (GC=1, UC=0), CAPRA-S_{*i*} is that subjects' CAPRA-S score (0-12), GC_{*i*} is the GC score (0-1), $\beta_0 \sim N(\mu, \sigma^2)$ and

$\phi_k \sim N(0, \sigma^2)$ are random cluster and period effects, respectively. The null hypothesis $\beta_2 = 0$ will be tested using a Type III test (SAS PROC GLIMMIX) at a 0.05 significance level. 95% confidence intervals using robust variance estimates will also be calculated.

In addition to the model described above, an additional model including a group-by-period interaction term will be fit to ensure that group assignment in a period is not effected by preceding or subsequent periods. For the purposes of this analysis, the period effect will be

considered fixed. This may detect carry-over effects if behaviors or attitudes of physicians within sites persist or change over the course of the study or if changes in patient education materials or their presentation change from one period to the next. Should this interaction term be significant, an alternative analysis utilizing non-consecutive periods may be used.

Descriptive statistics for various quantities, including raw treatment rates (and 95% confidence intervals) of adjuvant treatment and type of treatment (hormone and radiation) for discrete risk categories for both CAPRA-S (low-risk 0-4, high-risk ≥ 5) and GC (low-risk ≤ 0.45 , high-risk > 0.45) as well as by clinical center and period. Model-based predicted probabilities of treatment will be calculated for various combinations of CAPRA-S and GC high and low risk along with associated confidence intervals.

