One such assay is Decipher from GenomeDx Biosciences, a GC assay developed and validated in a post-RP setting as a predictor of eventual metastasis (Erho 2013). Studies have demonstrated independent prognostic value of this GC assay above and beyond standard clinicopathologic parameters reclassifying the clinically high-risk men tested into lower or significantly elevated risk of metastatic disease progression (Karnes 2013, Den 2014, Cooperberg 2015, Klein 2015, Den 2015, Ross 2015, Yamoah 2015). Studies have demonstrated that Decipher low risk patients can safely delay/defer treatment and avoid the adverse side effects of radiation treatment after radical prostatectomy while Decipher high risk patients can benefit from early adjuvant radiation (Den 2014, Den 2015).

In addition to clinical validation, several decision impact studies of Decipher were conducted to investigate a GC's influence on physicians' post-radical prostatectomy treatment recommendations (Badani 2013, Badani 2014, Michalopoulos 2014, Nguyen 2015).

Badani (2013) evaluated the influence on urologist treatment recommendations with GC in comparison to clinicopathologic risk factors alone for patients from a tertiary care center. This prospective, pre-post design study showed that among twenty-one high volume (i.e., mean 180 RP/year) urologic surgeons from 18 US institutions who were asked to make treatment recommendations for 24 prostate cancer patient cases post-RP, 43% changed their treatment recommendation with the addition of genomic information to standard clinicopathologic information.

To further reflect the distribution of test results and risk of metastasis among high-risk patients seen in a broader range of clinical settings other than academic centers, a prospective, multi-center, decision-impact study (ASSESS-D, Badani 2014) evaluated the effect of knowledge of the GC model on urologist treatment decision-making in a population of patients having undergone radical prostatectomy in a community-based practice. One hundred ten patient case histories were available for review by 51 urologists. Overall, 31% (95% CI: 27- 35%) of treatment recommendations changed with knowledge of GC. Treatment intensity was strongly correlated with the GC-predicted probability of metastasis ($p < 0.001$) and the GC was the dominant risk factor driving decisions in multivariable analysis (OR=8.6, 95% CI: 5.3-14.3%, $p < 0.0001$).

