2.1. Primary Study Objective

To determine the impact of GC test results on adjuvant treatment decisions of high-risk post-RP patients with undetectable post-op PSA compared to clinical factors alone. Specifically, determine whether higher GC risk increases the likelihood of receiving adjuvant treatment and lower GC risk decreases the likelihood of receiving adjuvant treatment compared to subjects with similar CAPRA-S score who do not have the GC test.

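### The primary test (beta2) is a GC-score slope within the GC arm; it measures the effect of disclosing the score only if usual-care men have no such slope, which the plan never checks

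*Combined protocol and SAP*

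**What the plan says.** Section 2.1 sets a comparison between arms, in two directions: a higher GC risk should raise the chance of adjuvant treatment and a lower one reduce it, "compared to subjects with similar CAPRA-S score who do not have the GC test". Section 3 says that in usual-care (UC) periods "only the CAPRA-S results, provided by MUSIC-Central, will be available".

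Section 7.1 states how the objective is tested: "This will be evaluated by testing for an effect of GC score in a regression model which adjusts for CAPRA-S risk score". It fits a logistic mixed model with fixed effects for arm (GC = 1, UC = 0), arm times GC score, and CAPRA-S, plus random centre and period effects. The primary test is beta2 = 0 for the arm-times-score term, at 0.05. The only additional primary model adds a group-by-period term. The Secondary Objective 2 model in 7.3 has no GC main effect either.

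Three other places bear on the point:

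- Section 6.1: FFPE tissue "will be collected from patients in both the GC and UC arms for transcriptome-wide expression analysis".
- Sections 4.1, 5.1 and 3.4: men enter with "PSA <0.1 ng/ml at enrollment". On the endpoint, "Adjuvant will be defined as preceding BCR" (PSA 0.2 or more) and within 18 months of surgery. The data collected include "All available post-op PSA levels", but PSA is not in the model.
- Section 7.5.2: 83% power with 350 subjects. Section 3 plans 550.

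**The concern.** A significant beta2 will be read as showing that the GC result changes treatment. The model supports that reading only through a constraint: UC men contribute no GC slope, because the model gives them none.

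A slope can exist without disclosure. Section 1 credits the test with "independent prognostic value of this GC assay above and beyond standard clinicopathologic parameters". Treatment prompted by a PSA rise that is still below 0.2 counts as adjuvant and could track GC in both arms. Physicians also see Gleason pattern, margins, extra-prostatic extension and seminal vesicle invasion, which a linear CAPRA-S total may not fully capture. The documents quantify neither route.

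If such a slope exists, the test can reject although disclosure changed nothing, and the stated outputs would not clearly show it. The raw rates by GC category (7.1) and the empirical probabilities (7.3) are not said to be split by arm. Model-based predictions cannot vary with GC within UC.

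**Working it through.** **1. What beta2 is.** Setting G = 1 gives a GC slope of beta2. Setting G = 0 gives zero by construction. The effect of disclosure on the slope is slope(GC arm) minus slope(UC arm), which equals beta2 only if the UC slope, given CAPRA-S, is zero.

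**2. Inputs.** From 7.5 to 7.5.2: odds ratios of 1.47 (GC), 1.15 (CAPRA-S) and 0.24 (arm); about 8% treated among CAPRA-S high-risk men; site ICC 23%; period ICC 3%; the printed site rates; 3-month periods. Site variance 1 gives 1/(1 + 3.29) = 23.3%, which matches the plan. Assumed, because the documents do not give them: the 1.47 is per 0.1 of score; GC score is beta-distributed with mean 0.42; its correlation with CAPRA-S is 0.4; site 5 enrols 4 per month. The test is a two-sided Wald test with variance components held at planning values.

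**3. The plan's own figure.** The 83% cannot be reproduced from stated inputs alone. With the GC standard deviation (SD) tuned to 0.245, 8 sites and a zero UC slope:

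| N | 200 | 250 | 300 | 350 | 400 | 500 |
|---|---|---|---|---|---|---|
| Table 1 | 47% | 60% | 77% | 83% | 88% | 93% |
| Simulated | 58% | 69% | 78% | 83% | 88% | 93% |

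The match is close from 300 up and too high at 200-250. Reading 1.47 per 1.0 of score gives only about 2% rejection, so per 0.1 is the workable reading.

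**4. No disclosure effect.** Arm effect zero, the same GC slope in both arms, N = 550, 14 sites, SD 0.245:

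| Shared GC odds ratio per 0.1 | Test as written | With GC main effect |
|---|---|---|
| 1.0 | 4.5% | 4.5% |
| 1.1 | 11% | 5.0% |
| 1.2 | 33% | 4.3% |

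Other settings tuned to the 83%, with 6 to 12% treated, give 13-14% and 35-38% at odds ratios 1.1 and 1.2. Varying the GC mean (0.35-0.50) or the correlation (0.2-0.6) gives 11-15% and 26-42%. An SD of 0.22, not tuned to the 83%, gives 10% and 28%.

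Hand check: the median beta2 estimate is 0.084 per 0.1 at odds ratio 1.1 and 0.163 at 1.2. The standard error of one arm's slope is about 0.105. At 1.1, 0.084/0.105 = 0.80, so rejection is about 13%. At 1.2, 0.163/0.105 = 1.55, so about 34%.

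**5. Power for the slope difference.** True UC slope zero, GC-arm odds ratio 1.47, so ln 1.47 = 0.385 per 0.1. At 550 the test as written has about 96% power, which implies z = 1.96 + 1.74 = 3.70 and a standard error of 0.385/3.70 = 0.104. Adding the UC slope's error gives sqrt(0.104² + 0.105²) = 0.148. Then 0.385/0.148 = 2.60, and power is Phi(2.60 - 1.96) = 74%.

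Simulation gives about 72-74% at 550 and 52-59% at 350. Over SD 0.18-0.26 it gives 47-76% at 550; at SD 0.18 the test as written itself has only 60% at 350. Reaching 80% would take about 650-700.

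**6. Testing the UC slope.** With a standard error of 0.10-0.11 per 0.1, the 95% CI at 550 multiplies and divides the odds ratio by about 1.21-1.25. Power to detect a UC odds ratio of 1.1 is about 15%, and of 1.2 about 41%.

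**7. Direction.** As the model is written, the log odds ratio of GC versus UC care at score g is beta1 + beta2 × g. Read per 0.1, the planning values change sign at 1.427/3.853 = 0.37 (ln 0.24 = -1.427). Read per 1.0, the odds ratio runs from 0.24 to 0.24 × 1.47 = 0.35: treatment falls at every score although beta2 is positive. A slope alone does not establish the two-way claim in 2.1.

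**The case against.** The strongest defence is that UC physicians and patients never see the score, so a zero UC slope is the natural starting assumption. The PSA route is narrow: treatment must follow enrolment below 0.1, precede 0.2 and fall within 18 months of surgery. That the score predicts outcome does not show that it drives treatment when undisclosed. All of this stands.

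It can also be said that 2.1 compares with men of similar CAPRA-S, not similar GC score, so a UC reference that depends on CAPRA-S alone follows the text. That is a fair literal reading. But comparing high-GC men with UC men of all GC scores is not a like-for-like randomised contrast, and attributing the difference to the test result still needs the zero slope.

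The list of summaries in 7.1 is open-ended, so an arm split is not excluded; it is only not stated. Resting the main claim on the slope difference would also cost much power, and that counts against requiring it.

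**Conclusion.** The point holds as a gap that should be closed. Beta2 is a within-GC-arm association, its reading as a disclosure effect rests on one plausible assumption, and no planned analysis is stated to check it. The sizes are conditional: about 11-15% or 26-42% rejection at 550 with no disclosure effect, if both arms share a GC odds ratio of 1.1 or 1.2 per 0.1. Those shared odds ratios, the per-0.1 unit and the GC distribution are assumptions.

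A reader might infer that the primary test is invalid, or that the slope difference must replace it. The documents do not support either. They give no UC slope, the score is withheld in UC, and with a zero UC slope the planned test is valid. Replacing the test is a trade-off against power that the sponsor may decline.

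The Secondary Objective 2 model also lacks lower-order terms. However, its tested three-way term does not match its stated hypothesis (GC test use by CAPRA-S). That is a separate defect, which adding lower-order terms alone would not repair.

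**What to change.** 1. Keep the 7.1 test of beta2 as the formal test if wished, but describe it as the association between GC score and treatment within the GC arm.
2. Prespecify a supporting model: logit(pi) = b0 + b1 G + b2 (G × GC) + b3 CAPRA-S + b5 GC + centre + period. Report the UC slope (b5) and the difference in slopes (b2), each with its 95% CI. Do not treat a non-significant b5 as proof that it is zero.
3. Report treatment rates by arm within GC above 0.45 and at or below 0.45, and the model-based GC-versus-UC contrast at low and high GC, so that both directions in 2.1 are shown.
4. State in 7.5.2 that the 83% is power for the within-arm slope. Give the lower power for the slope difference from the sponsor's own simulation, with the unit of the 1.47 and the GC distribution used.
5. State that UC tissue collected under 6.1 is scored and that the scores stay undisclosed until the endpoint is fixed. Section 6.5 describes one unchanged assay for all patients but does not clearly say that UC men are scored.

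Cost: more analysis and a less precise supporting contrast. No added enrolment is asked for. If 6.5 was not meant to cover UC men, the cost of assaying them is a further downside.
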